**Table 6      Laboratory Assays**

Sampling Time Points	System	Component	Method	Unit	Number of Subjects
Humoral immunity					
Month 3, Month 10, and Month 11	Serum	anti-PRP antibody	ELISA a	µg/mL	All
CCI					
CCI					
ELISA=enzyme linked immunosorbent assay					
CCI					

## 8.2      Safety Assessments

The investigator and any designees are responsible for detecting, documenting, and reporting events that meet the definition of an AE or SAE [Appendix 4]. The investigator and any designees remain responsible for following up AEs that are serious, considered related to the study intervention or the study, or that caused the subject to discontinue the study intervention or discontinue from study.

### 8.2.1      Physical Examinations

- A brief history-directed physical examination will include, at a minimum, assessment of body temperature and vital signs.
- Investigators should pay special attention to clinical signs related to previous serious illnesses.
- Subject vaccination history and maternal dTpa immunisation history will be collected.

### 8.2.2      Vital Signs

Temperature will be taken before each vaccination (i.e., at Visit 1, Visit 2 and Visit 4). Rectal temperature is preferred, but oral or axillary temperature is also allowed. Fever is defined as  $\geq 38^{\circ}\text{C}$ , regardless of route.

If the subject has a fever, the vaccination should be postponed and a new visit scheduled considering the allowed visit windows.

## 8.3 Adverse Events

### 8.3.1 Time Period and Frequency for Collecting AE and SAE Information

All SAEs will be collected from Visit 1 through study end, at the time points specified in the SoA [[Table 3](#)].

All AEs will be collected from vaccination through the 31-day follow-up period after each vaccination, as specified in the SoA [[Table 3](#)].

Medical occurrences that begin before the start of study treatment but after obtaining informed consent will be recorded on the Medical History/Current Medical Conditions section of the eCRF, not the AE section.

All SAEs will be recorded and reported to the Sponsor or designee within 24 hours, as indicated in [Appendix 4](#). The investigator will submit any updated SAE data to the Sponsor within 24 hours of it being available.

Investigators are not obligated to actively seek AEs or SAEs after conclusion of the study participation. However, if the investigator learns of any SAE, including a death, at any time after a subject has been discharged from the study, and he/she considers the event to be reasonably related to the study treatment or study participation, the investigator must promptly notify the Sponsor.

The method of recording, evaluating, and assessing the causality of AEs and SAEs and the procedures for completing and transmitting SAE reports are provided in [Appendix 4](#).

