### 1.3 Schedule of Activities

**Table 3 Schedule of Activities**

Age	2 Months	4 Months	5 Months	12 Months	13 Months
Study phase	Study phase 1 (Primary)			Study phase 2 (Booster)	
Type of contact	Visit 1	Visit 2	Visit 3	Visit 4	Visit 5
Sampling time points			Post-primary	Pre-booster	Post-booster
Informed consent by parents/LAR(s)	●				
Check inclusion/exclusion criteria	●				
Check contraindications to vaccination	○	○		○	
Collect demographic data (including gestational age)	●				
Vaccination history and maternal dTpa immunisation	●				
Vaccines					
Study group and treatment number allocation	○				
Treatment number allocation for subsequent doses		○		○	
Recording of administered treatment number	●	●		●	
Vaccine administration	●	●		●	
Clinical specimens for laboratory assays					
Blood sampling for antibody determination (~2.5 mL)			●	●	●

Age	2 Months	4 Months	5 Months	12 Months	13 Months
Study phase	Study phase 01 (Primary)			Study phase 02 (Booster)	
Type of contact	Visit 1	Visit 2	Visit 3	Visit 4	Visit 5
Sampling time points			Post-primary	Pre-booster	Post-booster
Safety assessments					
Medical history	●				
Check contraindications, warnings and precautions to vaccination	○	●		●	
Pre-vaccination body temperature a	●	●		●	
Record any concomitant medication/vaccination	●	●	●	●	●
Distribution of memory aids	○	○		○	
Return of memory aids		○	○		○
Recording of unsolicited AEs b (including the review of memory aids)	●	●	●	●	●
Reporting of SAEs c	●	●	●	●	●
Study Conclusion					●

AEs=adverse events; SAEs=serious adverse events; dTpa=combined reduced-antigen-content diphtheria, tetanus and acellular pertussis; LAR=legally acceptable representative.

a Fever is defined as temperature  $\geq 38^{\circ}\text{C}$  (regardless of route). Rectal temperature is preferred, but oral or axillary temperature is also allowed.

b AEs collected during 31-day follow-up period after each vaccination.

c SAEs collected throughout study.

● = study procedure that requires documentation in the individual eCRF.

○ = study procedure that does not require documentation in the individual eCRF.

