## 4.0 STUDY DESIGN

### 4.1 Overall Design

This is a phase IV, single-blind, randomised, controlled and multi-country study in infants and toddlers 6 to 12 weeks of age at the time of first vaccination.

The subjects will be assigned to 1 of 2 parallel groups:

- Inv\_group (Investigational group): All subjects in this group will receive 3 doses (2 primary doses+1 booster dose) of *Infanrix hexa* co-administered with 3 doses of *Prevenar 13* at 2, 4, and 12 months.
- Com\_group (Comparator group): All subjects in this group will receive 3 doses (2 primary doses+1 booster dose) of *Vaxelis* co-administered with 3 doses of *Prevenar 13* at 2, 4, and 12 months.

Duration of the study: The intended duration of the study per subject is approximately 11 months, divided into 2 study phases.

- Study phase 1: Primary study phase, starting at Visit 1 (Day 1) and ending at Visit 3 (Month 3), i.e., 1 month following the second primary dose.
- Study phase 2: Booster study phase, starting at Visit 4 (Month 10) and ending at Visit 5 (Month 11), i.e., 1 month after the booster dose.

Treatment allocation: The subjects will be randomised at a 1:1 ratio to Inv\_group or Com\_group using a minimisation algorithm with the study country and maternal immunisation status as minimisation factors. This will be done at study entry using an Interactive Voice Response System (IVRS) randomisation.

Proposed countries: About 3 European countries.

Sampling schedule: Blood samples will be collected from all subjects at the following time points:

- Post-Primary (Visit 3): At 1 month after the second dose of primary vaccination, a volume of approximately 2.5 mL of whole blood will be collected.
- Pre-Booster (Visit 4): Before the administration of the booster dose, a volume of approximately 2.5 mL of whole blood will be collected.
- Post-Booster (Visit 5): At 1 month after the booster vaccination, a volume of approximately 2.5 mL of whole blood will be collected.

Data collection: electronic Case Report Form (eCRF).

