## 7.4 Reason for Discontinuation

Subjects may be withdrawn from the treatment and the study for any of the following reasons:

- The parents or LARs withdraw consent on behalf of the subject.
- The parents or LARs are unwilling or unable to comply with the protocol.
- Adverse event(s).
- Lost to follow-up.
- Protocol deviation(s).
- Occurrence of contraindications that were not present at enrolment.
- If, in the clinical judgment of the investigator, it is not in the subject's best interest to continue with the study treatment.

The reason for the subject's withdrawal from the study or from treatment must be recorded in the subject's eCRF. When a subject is withdrawn, the date of last contact and reason for treatment/study withdrawal (see above) should be clearly described in the relevant sections of the eCRF. If a subject is removed from study or treatment because of an AE, the reason for treatment withdrawal should always be stated as "adverse event" irrespective of whether this was the investigator's or the parents' or LARs' decision. The subject should be followed until the event has resolved, stabilised, or returned to baseline.

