17.1.3. UNSOLICITED AE, EXCLUDING SAEs

For each study treatment, the incidence rates (frequencies and percentages) of subjects with unsolicited AEs, excluding serious AE, occurring within 31-days (Days 1-31) follow-up period after any dose will be presented by System Organ Class (SOC) and Preferred Term (PT) without 95% Clopper Pearson exact CI. The number of events defined as the number of PT with different start date will be included in the summary. This summary is needed for web posting and will not be part of the study report. Unsolicited AEs excluding SAEs will be recorded on the “Non-Serious Adverse Events and Intercurrent Medical Conditions” pages of the eCRF.

Listings of AEs and SAEs leading to withdrawal of study treatment and AEs and SAEs leading to death will be provided.

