APPENDIX 1. PROGRAMMING CONVENTIONS FOR OUTPUTS

IQVIA OUTPUT CONVENTIONS

Outputs will be presented according to the following IQVIA Output Conventions

Document Headers

All TFL is to include the following header:

GSK Vaccines
Vaccine: *Infanrix hexa*
Study 212645 (DTPa-HBV-IPV-141) - *DELIVERY DESIGNATION*

where delivery designation is the name of the current delivery, e.g., DRY-RUN, FINAL ANALYSIS REPORT, etc

DATES

Depending on data available, dates will take the form yyyy-mm-dd.

ATTRIBUTING EVENTS TO VACCINE DOSES

The dose relative to an event is the most recent study dose given to a subject prior to the start of a given event. For example, if the start date of an adverse event is between Dose 1 and Dose 2, the relative dose will be Dose 1. If an event starts on the same day as a study dose, the relative dose will be derived from the additional information provided in the case report form (CRF) using the contents of the flag indicating if the event occurred before or after study dose. If 'after study dose' is selected, the relative dose for the event will be the one administered on the start day of the event. If 'before study dose' is selected, the relative dose for the event will be the dose prior to this one.

ONSET DAY

The onset day for an event (e.g. AE, concomitant medication/vaccination) is the number of days between the last study dose and the start date of the event. This is 1 for an event occurring on the same day as a study dose (and reported as starting after study dose).

Document : \quintiles.net\enterprise\Apps\sasdata\SASb\SAS\GSK\Infanrix\PPD\Biostatistics\Documentation\NSAP

Author: PPD Version Number: 1.0

Version Date: [07JAN2021]

Template No.: CS_TP_BS016 Revision 6 Reference: CS_WI_BS005

Effective Date: 02Dec2019

SPELLING FORMAT

English UK.

PRESENTATION OF TREATMENT GROUPS

For outputs, treatment groups will be represented as follows and in the given order:

Vaccine Group	For Table, Listings and Figures
Infanrix hexa	Infanrix hexa
Vaxelis	Vaxelis
Prevenar 13	Prevenar 13

PRESENTATION OF VISITS

For outputs, visits will be represented as follows and in that order:

Long Name (default)	Short Name
Visit 1	V1
Visit 2	V2
Visit 3	V3
Visit 4	V4
Visit 5	V5

LISTINGS

All listings will be ordered by the following (unless otherwise indicated in the template):

- Vaccine group (or intervention received if it's a safety output),
- Center-subject ID,
- Date (where applicable),

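### Non-serious AEs that lead to stopping vaccination or leaving the study have no collection period outside Days 1-31 after each dose, so the promised withdrawal listing may be incomplete

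*Protocol*

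**What the plan says.** Two collection periods are set in Protocol 8.3.1. For serious events, "All SAEs will be collected from Visit 1 through study end". For the rest, "All AEs will be collected from vaccination through the 31-day follow-up period after each vaccination". Footnote b of the Schedule of Activities (Protocol Table 3) puts the same limit on the unsolicited AE row at every visit: "AEs collected during 31-day follow-up period after each vaccination". The secondary safety endpoint in Protocol 3.0 uses the same Days 1-31 period. None of these places mentions AEs that lead to discontinuation.

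Three other places deal with exactly those AEs and set no time limit:

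- Protocol 7.4 fixes how the reason is coded: "If a subject is removed from study or treatment because of an AE, the reason for treatment withdrawal should always be stated as" an adverse event, whoever took the decision. It then requires follow-up until the event resolves, stabilises or returns to baseline.
- Protocol 8.2 keeps the investigator responsible for following AEs that are serious, that are related, "or that caused the subject to discontinue the study intervention or discontinue from study".
- SAP 17.1.3 promises "Listings of AEs and SAEs leading to withdrawal of study treatment". Unlike the tabulations in SAP 17.1.1 and 17.1.3, that sentence carries no day limit.

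**The concern.** The plan requires one category of event to be attributed, followed and listed, but for most of the time before the booster it has no rule for recording the event. Take an infant with a non-serious event in the months between Visit 3 and Visit 4, whose parents or investigator then decide against the booster. Under 7.4 the site records the withdrawal as due to an adverse event. Under 8.3.1 and Table 3 the onset falls outside the AE collection period, so a site following those rules has no instruction to open an AE record.

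At stake is a descriptive safety output. The disposition table could show an infant withdrawn for an AE while the listing has no matching entry. The reader of the study report would then not know what the event was, when it began, how severe it was, or whether the investigator thought it related to the vaccine. Safety is a secondary objective, and the investigator knows which vaccine was given (Protocol 6.4.2), so details of AE-driven withdrawals by group are worth having.

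**Working it through.** **Inputs**

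- Day count: in SAP Appendix 1, on the onset day, "This is 1 for an event occurring on the same day as a study dose". Day 31 is therefore dose date + 30, and each window covers 31 calendar days.
- Visit timing (Protocol Table 8): age at Visit 1 42 to 84 days; Visit 1 to Visit 2 nominal 60, allowed 52 to 78; Visit 4 at age 365, allowed 335 to 395; Visit 4 to Visit 5 nominal 30.
- Assumption: Table 8 gives no single nominal age in days for Visit 1. I use 61 days (2 months) and 63 days (midpoint of 42 and 84).

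**Check against the plan's own timeline.** With Visit 1 at 61 days and 30.4375 days per month:

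- Visit 3: (60 + 30) / 30.4375 = 2.96 months
- Visit 4: (365 − 61) / 30.4375 = 9.99 months
- Visit 5: (365 − 61 + 30) / 30.4375 = 10.97 months

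These match the stated Months 3, 10 and 11. The plan gives no figure of its own for the uncovered time.

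**Gap between Doses 1 and 2** = (Visit 1 to Visit 2 interval) − 31

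- Nominal: 60 − 31 = 29 days
- Range: 52 − 31 = 21 to 78 − 31 = 47 days

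**Gap between Dose 2 and booster** = (age at Visit 4) − (age at Visit 1 + Visit 1 to Visit 2 interval) − 31

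- Visit 1 at 63 days: 365 − (63 + 60) − 31 = 211 days
- Visit 1 at 61 days: 365 − (61 + 60) − 31 = 213 days (7.0 months)
- Shortest: 335 − (84 + 78) − 31 = 142 days (4.7 months)
- Longest: 395 − (42 + 52) − 31 = 270 days (8.9 months)

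**Both gaps together**, Visit 1 at 63 days: 29 + 211 = 240 days, out of 365 − 63 + 30 = 332 days of follow-up, or 72%. This is calendar time only. It is not a proportion of infants or of events.

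**What is assured for a non-serious onset in a gap**

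| Item | Assured? | Basis |
|---|---|---|
| Withdrawal, date of last contact, reason coded as adverse event | Yes | Protocol 7.4 |
| Follow-up of the event | Required | Protocol 7.4, 8.2 |
| AE term, onset date, intensity, causality, outcome | No | Outside the period in 8.3.1 and Table 3 footnote b |

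**Other capture routes.** Memory aids are returned at Visits 2, 3 and 5 but not at Visit 4 (Table 3), so none is collected at the end of the long gap. Medication linked to a non-serious AE is generally recorded only for Days 1 to 31 (Protocol 6.6). The eCRF page for non-serious AEs also takes intercurrent medical conditions (SAP 17.1.3), but the Protocol glossary confines these to conditions able to alter the immune response or confirmed immunodeficiency. Protocol 8.3.2 brings laboratory changes during the study into the AE section, and laboratory changes only. Appendix 4 of the Protocol tells investigators to record AE details in general terms, but 8.3.1 is the specific rule on the collection period.

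**The case against.** The strongest reply is that 7.4 and 8.2 are specific rules that sit alongside the general window, so a careful site would record the event anyway. Protocol 7.4 wants the reason clearly described in the eCRF, and 9.4.5 says that data from withdrawn subjects, AEs included, enter the analyses. For an infant who attends Visit 4, Table 3 has a contraindications row that must be documented in the eCRF, and Protocol 6.5 requires departures from the regimen to be recorded. Many of the neurological or allergic events that would stop vaccination are SAEs in any case: Protocol Appendix 4 names convulsions without hospitalisation and intensively treated allergic bronchospasm, and SAEs are collected throughout.

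Much of this stands, and it rules out three stronger readings that a reader might infer:

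- *That such events are never recorded.* The withdrawal and its attribution to an AE are recorded at any time under 7.4.
- *That the listing will omit them.* The listing sentence in SAP 17.1.3 has no day limit, and some sites may enter the event. The documents support only that it may be incomplete.
- *That this is an unrecorded source of differential dropout.* The reason is recorded, and discontinuation reasons are presented (Protocol 9.4.1, SAP 9.1), so AE-related loss can be counted by group.

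What the reply does not supply is a sentence giving these AEs a collection period outside Days 1-31. Two site teams could read the current text differently and both be compliant.

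**Conclusion.** The point holds as an inconsistency in the collection rules. Protocol 8.3.1 and Table 3 footnote b do not fit with 7.4, 8.2 and SAP 17.1.3. About 29 days between Doses 1 and 2 and about 211 to 213 days before the booster (142 to 270 across the allowed windows) have no collection rule for non-serious AEs leading to discontinuation. The nominal figures rest on an assumed age of 61 or 63 days at Visit 1.

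The consequence is limited. For onsets in the gaps the eCRF is sure to hold only the disposition reason, so the listing may be incomplete and may not reconcile with the disposition reasons. The documents give no number of affected infants. It is probably small, since serious events are already covered. The 20% allowance for non-evaluable subjects in Protocol 9.2 covers all causes and says nothing about AE withdrawals. The SAP listing names withdrawal of study treatment and not withdrawal from the study, although an infant who leaves before the booster has also stopped treatment.

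The primary analysis is not altered. An infant without a booster has no post-booster titre after a third dose whether or not the AE is described, and missing titres are not replaced.

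**What to change.** Bring the passages into line:

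1. In Protocol 8.3.1 and Table 3 footnote b, state that any AE, serious or not, leading to discontinuation of study vaccine or withdrawal from the study is recorded from Dose 1 to study conclusion, whatever its onset day, with term, onset date, intensity, causality and outcome.
2. Keep the Days 1-31 rule for all other non-serious AEs. The secondary endpoint and the 31-day tabulations can stay as they are.
3. In SAP 17.1.3, run the listing over the whole study period, name withdrawal from the study as well as from study treatment, and reconcile it with the disposition reasons in SAP 9.1 by group.

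For this category the uncovered time then falls to zero. The cost is one sentence, one footnote, eCRF completion guidance and a line in the SAP, with no added visit or procedure. The downside is a few extra AE entries outside the 31-day windows.

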### 8.3.2 Method of Detecting AEs and SAEs

Memory aids used by subjects' parent(s)/LAR(s) will be reviewed for health related issues of subjects and for potential AEs which will be transcribed in eCRFs. Care will be taken not to introduce bias when detecting AEs and/or SAEs. Open-ended and nonleading verbal questioning of the subject's parents or LARs is the preferred method to inquire about AE occurrences.

For any unplanned/routine laboratory investigation performed, the investigator must review the laboratory report, document that he/she did so, and record any clinically relevant changes occurring during the study in the AE Section of the CRF/eCRF. Clinically significant abnormal laboratory findings are those which are not associated with an underlying disease, unless judged by the investigator to be more severe than expected for the participant's condition.

- All clinically significant abnormal laboratory test values during the study or within 31 days after the last dose of study intervention should be repeated until the values return to normal or baseline, or are no longer considered significantly abnormal by the investigator or LML. Refer to [Appendix 4](#) for more information on clinically abnormal laboratory assessments that qualify as an AE or SAE.

- If such values do not return to normal/baseline after an interval judged reasonable by the investigator, the aetiology should be identified and the sponsor notified.

### **8.3.3 Follow-up of AEs and SAEs**

After the initial AE/SAE report, the investigator is required to proactively follow each subject at subsequent visits/contacts. All SAEs will be followed until resolution, stabilisation, the event is otherwise explained, or the subject is lost to follow-up (as defined in [Section 7.3](#)). Further information on follow-up procedures is given in [Appendix 4](#).

### **8.3.4 Regulatory Reporting Requirements for SAEs**

- Prompt notification by the investigator to the Sponsor of an SAE is essential so that legal obligations and ethical responsibilities towards the safety of subjects and the safety of a study treatment under clinical investigation are met. For SAEs, the investigator will always provide an assessment of causality at the time of the initial report, as defined in the [Appendix 4](#).
- The Sponsor has a legal responsibility to notify both the local regulatory authority and other regulatory agencies about the safety of a study treatment under clinical investigation. The Sponsor will comply with country-specific regulatory requirements relating to safety reporting to the regulatory authority, IRB/IEC, and investigators.
- Investigator safety reports must be prepared for suspected unexpected serious adverse reactions (SUSAR) according to local regulatory requirements and Sponsor policy and forwarded to investigators as necessary.
- An investigator who receives an investigator safety report describing an SAE or other specific safety information (e.g., summary or listing of SAEs) from the Sponsor will review and then file it and will notify the IRB/IEC, if appropriate according to local requirements.

### **8.3.5 Subject Card**

The investigator (or designee) must provide the subjects' parent(s)/LAR(s) with a "subject card" containing information about the clinical study. The subject's parent(s)/LAR(s) must be instructed to keep the subject card in his/her/their possession at all times throughout the study. In an emergency, this card serves to inform the responsible attending physician/LAR/care giver/family member that the subject is in a clinical study and that relevant information may be obtained by contacting the investigator.

